## 8.2. Setting

Adult patients (age  $\geq 18$  years) hospitalized for NVAf, based on a primary or secondary discharge diagnosis code indicating NVAf, will be identified from the Premier Hospital database between January 1, 2013 and June 30, 2017. Patients who received apixaban, dabigatran, rivaroxaban, or warfarin during any time of the hospitalization (from admission to discharge) will be identified and grouped into study cohorts based on the OAC initiated. The first of such NVAf hospitalizations will be defined as the index hospitalization, with the corresponding hospital discharge date as the index date.

### 8.2.1. Inclusion criteria

Patients must meet all the following inclusion criteria to be eligible for inclusion in the study:

- Have a hospital discharge ICD-9-CM code of 427.31 or 427.32 (and corresponding ICD-10 codes) indicating a primary or secondary diagnosis of AF identified from the Premier Hospital database between January 1, 2013 and September 30, 2017.
- Received any of the OACs, apixaban, dabigatran, rivaroxaban, or warfarin during any time of the hospitalization from admission to discharge
- Have an age  $\geq 18$  years as of the initial hospitalization with an AF diagnosis

Note: All the medical codings, e.g. ICD-9, ICD-10, CPT/HCPCS codes used in the patient selection criteria are consistent with the Eliquis Harmonized Retrospective Study Protocol.

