### 3. ABSTRACT

**Title:** Hospital Readmissions Among Nonvalvular Atrial Fibrillation Patients Treated with Oral Anticoagulants in the U.S.

**Version:** 1

**Date of Protocol:** March 26, 2018

**Author:** [name], MBA, Novosys Health; [name], JD, MPH, Pfizer

**Rationale and background:** Hospital readmission rates are a critical concern in the U.S. and in October of 2012 the Hospital Readmissions Reduction Program was implemented by the Centers for Medicare and Medicaid Services (CMS) to reduce the frequency of readmission among Medicare patients. It has therefore become increasingly important to examine hospital readmission rates and the factors associated with readmission. Although, readmission rates of NVAF patients have been studied to some extent in regard to all-cause readmissions, little information exists in the published literature on bleeding-related readmissions. We previously conducted an early evaluation that investigated rates of all-cause and bleeding-related readmissions among NVAF patients treated with dabigatran, rivaroxaban, and apixaban (January 1, 2012 through March 31, 2014). This current analysis will be a follow-up of our earlier assessment and will include in addition to NVAF patients treated with DOACs, patients treated with warfarin. Patients hospitalized for NVAF and treated with OACs will be identified from January 1, 2013 through June 30, 2017.

**Research question:** What is the frequency of readmission for major bleeding (MB) within 1 month after an index hospitalization for nonvalvular atrial fibrillation (NVAF) for patients treated with apixaban, dabigatran, rivaroxaban, or warfarin?

Note: we anticipate that the sample size of patients treated with edoxaban is low and thus do not include edoxaban in this study evaluation. This is consistent with previous alliance NVAF studies.

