recent patient data from 2007 to 2008), little information exists in the published literature on bleeding-related readmissions. In the real-world setting bleeding is a significant burden healthwise and economic wise and represents a critical target for improving the quality of care of NVAF patients. In clinical trials NVAF patients treated with the different DOACs differed in bleeding rates and the DOACs with lower bleeding risk have potentially a greater likelihood of improving the anticoagulation management of NVAF patients in the real-world setting where bleeding rates are higher than observed in the clinical trial setting. We previously conducted an early evaluation that investigated rates of all-cause and bleeding-related hospital readmissions among NVAF patients treated with dabigatran, rivaroxaban, and apixaban (January 1, 2012 through March 31, 2014). In this early analysis of 74,730 patients identified from the Premier Hospital database, after controlling for differences in patient characteristics, compared with patients who received apixaban during their index hospitalizations, the odds of bleeding-related hospital readmissions were significantly greater by 1.4-fold ( $p < 0.01$ ) for patients who received rivaroxaban and 1.2-fold ( $p = 0.16$ ) numerically trending greater for patients who received dabigatran. This current analysis will be a follow-up of our earlier assessment and will include patients treated with warfarin in addition to NVAF patients treated with DOACs. Recent real-world evidence has suggested that unmeasured or unmeasurable secular trends in prescribing patterns may contribute to differential outcomes observed with DOACs. For this study, patients hospitalized for NVAF and treated with OACs will be identified from January 1, 2013 through June 30, 2017, a time period in which dabigatran, rivaroxaban, and apixaban were all available, and 1- and 3-month readmission outcomes will be evaluated.

This non-interventional study is designated as a Post-Authorisation Safety Study (PASS) and is conducted voluntarily by Pfizer.

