## **8. RESEARCH METHODS**

### **8.1. Study design**

The study will be a retrospective cohort analysis using the Premier Hospital database. The overall study period will be from January 1, 2012 through September 30, 2017, to allow for a 1 month follow up period for observation of readmissions and a 1-year baseline observation period. Adult patients (age  $\geq 18$  years) hospitalized for NVAF, based on a primary or secondary discharge diagnosis code indicating NVAF, will be identified from the Premier Hospital database between January 1, 2013 and June 30, 2017. Patients who received apixaban, dabigatran, rivaroxaban, or warfarin during any time of the hospitalization (from admission to discharge) will be identified and grouped into study cohorts based on the OAC initiated. The first of such NVAF hospitalizations will be defined as the index hospitalization. Patients with more than one type of OAC drug usage during the index hospitalizations will be excluded so that patients can be exclusively assigned into each OAC patient cohorts. Demographic, patient clinical characteristics, hospital characteristics, and key anticoagulant treatment-related information will be measured during the index hospitalization of NVAF patients. Other clinical characteristics (e.g. prior bleeding) of NVAF patients will be measured during a 12-month baseline period. The proportions of patients treated with apixaban, dabigatran, rivaroxaban, and warfarin that have MB-related, all-cause, and stroke-related readmissions that occur within 1 month of discharge of their initial hospitalization for NVAF will be evaluated. Hospital LOS and associated costs of MB-related, all-cause, and stroke-related readmissions will be determined and compared between the other OAC cohorts and the apixaban cohort.

Note: We anticipate that the sample size of patients treated with edoxaban is low and thus we have not included patients treated with edoxaban in this study evaluation. This is consistent with previous alliance NVAF studies.

**Figure 1. Study Time Periods** (for illustration purposes, may not be proportional)

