**Table 2. Outcome Measurements: Readmissions and Associated LOS and Cost/Charges**

Variable	Role	Operational definition
MB-related Readmission	Outcome	
Defined as readmissions with a bleeding diagnosis at the first position of the hospital discharge diagnosis codes.
 
Number and percentage of patients with MB-related readmissions within 1 or 3 months of initial NVAF hospitalization in study cohorts will be reported. Associated LOS and cost for MB-related readmissions will be determined. Likelihood of first MB-related readmission was assessed for each OAC cohort vs. the apixaban cohort. LOS and hospital cost per patient for cohorts will be estimated and compared by multivariable regression analysis. Measurements for 3-month readmissions will be evaluated using descriptive statistics as an exploratory analysis.

All-cause Readmission	Outcome	
Number and percentage of patients with all-cause readmissions within 1 or 3 months of initial NVAF hospitalization in study cohorts will be reported. Associated LOS and cost for all-cause readmissions will be determined. Likelihood of first all-cause readmission was assessed for each OAC cohort vs. the apixaban cohort. LOS and hospital cost per patient for cohorts will be estimated and compared by multivariable regression analysis. Measurements for 3-month readmissions will be evaluated using descriptive statistics as an exploratory analysis.

Stroke-related Readmission	Outcome	
Defined as readmissions with a stroke diagnosis at the first position of the hospital discharge diagnosis codes. Cases will be excluded if traumatic brain injury (ICD-9: 800-804, 850-854) was present during hospitalization.
 
Number and percentage of patients with stroke-related readmissions within 1 or 3 months of initial NVAF hospitalization in study cohorts will be reported. Associated LOS and cost for stroke-related readmissions will be determined. Measurements for stroke-related readmissions will be evaluated using descriptive statistics as an exploratory analysis.

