### 8.7. Data analysis

Means  $\pm$  standard deviations, and medians will be provided for continuous variables. Numbers and percentages will be provided for dichotomous and polychotomous variables. Bivariate comparisons of baseline patient and hospital characteristics and readmission measurements will be provided, with appropriate tests (e.g., ANOVA test, chi-square test) used based on the distribution of the measure. A propensity score matching (PSM) 1:1 technique will be used to control for confounders when comparing each of the OAC cohorts vs. the apixaban cohort. A logistic regression analysis will be carried out on the matched patient cohorts to further evaluate the potential impact of treatment with the different OACs vs. treatment with apixaban on 1-month MB-related and all-cause readmissions. Only the index drug will be the covariate, since other patient characteristics are expected to be similar already after the PSM. Since the patient sample size attribution in the PSM process is not known, if the population sizes are not sufficient after the PSM attrition, a multivariable logistic regression analysis will be carried out to assess the potential impact of treatment with the different OACs compared to treatment with apixaban on 1-month MB-related and all-

cause readmissions, separately. The independent covariates in the regression analyses will include key patient demographics and hospital characteristics. The final list of such covariates will be determined with inputs from the Pfizer team. Additionally, we will carry out a two-part model analysis and a generalized linear model with log transformation and gamma distribution to examine the impact of treatment with the 3 different OACs vs. apixaban on MB-related and all-cause hospital readmission costs. Measurements related to exploratory objectives will be analyzed using descriptive statistics. All data analysis will be executed using statistical software SAS version 9.4.

Detailed methodology for summary and statistical analyses of data collected in this study will be documented in a Statistical Analysis Plan (SAP), which will be dated, filed and maintained by the sponsor. The SAP may modify the plans outlined in the protocol; any major modifications of primary endpoint definitions or their analyses would be reflected in a protocol amendment.

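### Section 8.2.1 ends patient identification on September 30, 2017, the end of the study period, whereas every other section ends it on June 30, so some admitted patients would have truncated outcome windows

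*Protocol*

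**What the plan says.** The protocol states the identification window six times.

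- Section 3 (Abstract), rationale: "Patients hospitalized for NVAF and treated with OACs will be identified from January 1, 2013 through June 30, 2017". The population paragraph of the same section gives the same end date.
- Section 6: "will be identified from January 1, 2013 through June 30, 2017, a time period in which dabigatran, rivaroxaban, and apixaban were all available".
- Section 8.1 gives June 30, 2017 as well.
- Section 8.2: patients "will be identified from the Premier Hospital database between January 1, 2013 and June 30, 2017".
- Section 8.2.1, the list of criteria that every patient must meet: "identified from the Premier Hospital database between January 1, 2013 and September 30, 2017".

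Five statements agree on June 30; only the inclusion criterion says September 30. Section 8.1 also fixes the outer limit: "The overall study period will be from January 1, 2012 through September 30, 2017". Section 8.2 starts follow-up at discharge, "with the corresponding hospital discharge date as the index date". Table 2 defines the outcome as a count: "Number and percentage of patients with MB-related readmissions within 1 or 3 months of initial NVAF hospitalization in study cohorts will be reported". For the 1-month comparison, section 8.7 states: "A logistic regression analysis will be carried out on the matched patient cohorts".

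**The concern.** Under section 8.2.1 a patient can be indexed on the day the study period closes. That patient has no time in which a readmission could be seen. Nothing in sections 8.2.1 or 8.2.2 requires a minimum observable period after discharge, and section 8.7 gives no censoring rule. A patient whose readmission falls after September 30, 2017 would stay in the denominator without an event, and the two-part cost model would record no readmission cost.

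Two things are at stake. First, the study population is defined in two ways, so two analysts could build different cohorts from the same protocol. Second, readmission rates would be somewhat too low. If one drug's cohort had a larger share of late discharges, the relative shortfall would be unequal between cohorts.

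**Working it through.** **Inputs.** Identification starts January 1, 2013 and ends June 30, 2017 (sections 3, 6, 8.1, 8.2) or September 30, 2017 (8.2.1). The study period ends September 30, 2017 (8.1). Follow-up starts at index discharge (8.2). Outcome windows are 1 month and 3 months (Table 2). The assumed 1-month major-bleeding readmission rate is 1.4%, the difference 0.5 points, and each cohort has at least 30,000 patients (8.5).

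**1. The plan's own sample size.** Taking 1.4% against 0.9%, two-sided alpha 0.05, 80% power and pooled variance under the null (mean rate 0.0115):

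n per arm = [1.960 × √(2 × 0.0115 × 0.9885) + 0.842 × √(0.014 × 0.986 + 0.009 × 0.991)]² / 0.005² = 7,137, or 14,274 for two arms.

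This is the Table 3 figure, reproduced as a two-arm total. It does not use the identification dates, so it is unchanged by this point. At 30,000 per arm the computed power for this difference exceeds 99%. The issue is therefore not power.

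**2. Length of the two windows.** To June 30: 1,642 days. To September 30: 1,734 days. Difference: 92 days, and 92 / 1,734 = 5.3%.

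**3. Who lacks a full window.** The protocol does not give a month in days; 30 and 90 days are assumed here.

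- 1 month: discharges on September 1 to 30, 2017 have 29 down to 0 days. That is 30 / 1,734 = 1.7% of index days. July and August discharges keep the full month.
- 3 months: discharges from July 3 to September 30, 2017 fall short. That is 90 / 1,734 = 5.2% of index days. Only July 1 and 2 are complete.

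Under uniform accrual (an assumption) these are also the shares of patients.

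**4. Events lost.** The shares in step 3 count patients with incomplete windows; they do not measure bias, because a partial window still yields events. Under constant hazard (an assumption), the loss is the average unobserved fraction of the window. For a window of w days it is (w + 1) / 2 ÷ 1,734.

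- 1 month: 15.5 / 1,734 = 0.9%. The rate reads 1.400% × (1 − 0.0089) = 1.387%, a shift of about 0.013 points. In a cohort of 30,000 that is about 4 of 420 expected events (30,000 × 0.014 = 420; 420 × 0.0089 = 3.7).
- 3 months: 45.5 / 1,734 = 2.6%.

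**5. Effect on the comparison.** If both cohorts have the same share of late discharges, both lose the same fraction of events. The ratio of rates is then essentially unchanged, and the 0.5-point difference becomes 0.5 × 0.9911 = 0.496. A distortion of the ratio needs unequal shares. With share s discharged in the last month and about half of their events lost, the rate reads 1.4% × (1 − 0.5s):

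| s (assumed) | Rate as read |
|---|---|
| 0.5% | 1.397% |
| 1% | 1.393% |
| 3% | 1.379% |
| 5% | 1.365% |

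Two cohorts with the same true rate of 1.4% at opposite ends of this range would differ by about 0.03 points.

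**6. After correction.** June 30 to September 30, 2017 is 92 days, so the last eligible discharge has both windows complete.

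**The case against.** The intended date is hardly in doubt. Five statements agree on June 30, one of them in section 8.2 directly above the criterion. If 8.2 and 8.2.1 are applied together, the two windows overlap only up to June 30. The September date looks like the study-period end carried into the wrong place. This stands, and it lowers the severity. It does not remove the conflict, because 8.2.1 is the list that decides eligibility.

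It is also fair to say that the protocol nowhere states that truncated patients count as not readmitted. That follows from a binary outcome with no follow-up rule, and section 8.7 leaves detailed methods to an SAP that may handle it. Likewise, September 30, 2017 is given as the end of the study period, not as the database cut-off. Both limits stand.

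A reader might infer more than the text supports. One inference is that all late patients lack primary follow-up; July and August discharges do not. Another is that the error favours apixaban because its use was rising. Section 6 mentions secular prescribing trends but gives neither direction nor size. Table 1 lists no calendar-time variable among the potential confounders, so the matching as described would not necessarily balance late discharges. That makes an unequal loss possible; it does not show one. Finally, the larger loss affects the 3-month outcomes, which are exploratory and only described.

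**Conclusion.** The inconsistency is real and lies in an operative eligibility date. Followed as written, section 8.2.1 admits patients whose outcome windows run past the end of the study period, and the stated analysis has nothing that would catch them. The expected effect on the primary rate is small: about 0.9% of 1-month events, or 0.013 points on 1.4%. For the 3-month outcomes it is about 2.6% of events. These figures rest on uniform accrual, constant hazard, 30- and 90-day windows, and no data used beyond September 30, 2017. A bias in the ratio between drugs is possible only if the cohorts' late shares differ, and the protocol supports no direction for it. This is an internal inconsistency of moderate-to-low severity, not a design choice.

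**What to change.** In section 8.2.1, replace the end date so that the criterion requires an index discharge date between January 1, 2013 and June 30, 2017, as in sections 3, 6, 8.1 and 8.2. Tying the criterion to discharge matters because follow-up starts there. Every patient then has 92 days to September 30, 2017, enough for both windows.

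The cost is one date. It excludes the July to September 2017 discharges, nearly all of whom cannot contribute complete 3-month outcomes and who are outside the population that the other sections describe. No new data are needed, and Table 3 stays as it is.

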### 8.2.2. Exclusion criteria

Patients meeting any of the following criteria with the records in the index hospitalizations will not be included in the study:

- Had medical claims indicating one of the following conditions or procedures during the index hospitalizations or within 12 months prior to the index date:
  1. Rheumatic mitral valvular heart disease or mitral valve stenosis:

- ICD-9 diagnosis codes 394.0, 394.1, 394.2, 394.9, 396.0, 396.1, 396.8, 396.9, 424.0
  - ICD-10 diagnosis codes I05.x, I08.0, I08.8, I08.9, and I34.x
2. Heart valve replacement/transplant:
- ICD-9 diagnosis codes V422 and V433
  - ICD-10 diagnosis codes Z95.2, Z95.3, Z95.4
  - ICD-9 procedure codes 35.05-35.09, 35.20-35.28, and 35.97
  - ICD-10 procedure codes 02RFx-02RJ0KZ, 02RJ4x, 02UG3JZ, and X2RFx
3. Dialysis, kidney transplant, or end-stage chronic kidney disease:
- ICD-9 diagnosis codes 585.6, 996.73, V45.1x, and V56.x
  - ICD-10 diagnosis codes N18.6, T82.8x8A, Z49.x, Z91.15, Z99.2
  - ICD-9 procedure codes 55.6x.
  - ICD-10 procedure codes 0TS00ZZ, 0TS10ZZ, and 0TYx.
  - Current Procedural Terminology (CPT) codes 90935, 90937, 90945, 90947, 90967 00868, 50300, 50320, 50323, 50325, 50327, 50328, 50329, 50340, 50360, 50365, and 50380
4. Venous thromboembolism (VTE):
- Deep vein thrombosis (DVT):
    - ICD-9 diagnosis codes 451-453, 671.3, 671.4, and 671.9
    - ICD-10 diagnosis codes I80.00-I82.91, O22.3x, O22.9x, O87.1, and O87.9
  - Pulmonary embolism (PE):
    - ICD-9 diagnosis codes 415.1, 673.2, and 673.8
    - ICD-10 diagnosis codes I26.x, O88.2x, O88.8x, T80.0XXA, T81.718A, T81.72XA, T82.817A, and T82.818A
5. Reversible AF:
- Pericarditis:
    - ICD-9 diagnosis codes 006.8, 017.9, 036.41, 074.21, 093.81, 098.83, 115.93, 390, 391, 392.0, 393, 411.0, 420.90, 420.91, 420.99, 423.0, 423.1, 423.2, 423.8, and 423.9
    - ICD-10 diagnosis codes A06.3, A06.8x, A17.83, A17.9, A18.82, A18.84, A18.89, A39.53, A52.06, A54.83, B33.23, B39.9, I00-I02.0, I09.2, I24.1, I30.x, I31.0, I31.1, I31.2, I31.3, I31.8, I31.9, I32
  - Hyperthyroidism or thyrotoxicity:
    - ICD-9 diagnosis codes 242.0, 242.1, 242.2, 242.3, 242.4, 242.8, and 242.9
    - ICD-10 diagnosis codes E05.x

- Acute myocardial infarction:
  - ICD-9 diagnosis codes 410.x
  - ICD-10 diagnosis codes I21.01-I21.4, and I22.x
- Acute myocarditis:
  - ICD-9 diagnosis codes 422.x
  - ICD-10 diagnosis codes A18.84, I40.x, and I41
- Had medical claims indicating a hip or knee replacement surgery during the index hospitalizations or within a 6-week period prior to the index date
  1. ICD-9 diagnosis codes V43.64 and V43.65
  2. ICD-10 diagnosis codes Z96.64x and Z96.65x
  3. ICD-9 procedure codes 81.40, 81.51, 81.52, 81.53, 81.54, and 81.55
  4. ICD-10 procedure codes 0SQ9x, 0SQBx, 0SR9019-0SR904Z, 0SR907Z, 0SR90Jz, 0SR90KZ, 0SRAx, 0SRB019-0SRB04Z, 0SRB07Z, 0SRB0Jx, 0SRB0KZ, 0SRC07Z, 0SRC0Jx, 0SRC0KZ, 0SRC0Lx, 0SRD07Z, 0SRD0Jx, 0SRD0KZ, 0SRD0Lx, 0SREx, 0SRRx-0SRWx, 0SW90JZ, 0SW93JZ, 0SW94JZ, 0SWA0JZ, 0SWA3JZ, 0SWA4JZ, 0SWB0JZ, 0SWB3JZ, 0SWB4JZ, 0SWC0JC, 0SWC0JZ, 0SWC3JC, 0SWC3JZ, 0SWC4JC, 0SWC4JZ, 0SWD0JC, 0SWD0JZ, 0SWD3JC, 0SWD3JZ, 0SWD4JC, 0SWD4JZ, 0SWE0JZ, 0SWE3JZ, 0SWE4JZ, 0SWR0JZ, 0SWR3JZ, 0SWR4JZ, 0SWS0JZ, 0SWS3JZ, 0SWS4JZ, 0SWT0JZ, 0SWT3JZ, 0SWT4JZ, 0SWU0JZ, 0SWU3JZ, 0SWU4JZ, 0SWV0JZ, 0SWV3JZ, 0SWV4JZ, 0SWW0JZ, 0SWW3JZ, and 0SWW4JZ.
- Had medical claims indicating pregnancy at any time during the study period
  1. ICD-9 diagnosis codes 630-679, V22, V23, V24, V27, V28, V61.6, V61.7, 792.3, and 796.5
  2. ICD-10 diagnosis codes A34, O00.00-O9A.53, Z33.1-Z37.9, Z39.x, and Z64.0
  3. ICD-9 procedure codes 72-75.9
  4. ICD-10 procedure codes 0DQPx-0DQQ8ZZ, 0DQRx, 0JCBx, 0Q82x, 0Q83x, 0TQBx, 0TQDx, 0U7C7ZZ, 0UCG0ZZ, 0UCG3ZZ, 0UCG4ZZ, 0UCM0ZZ, 0UJD7ZZ, 0UQ9x, 0UQCx, 0UQGx, 0UQMx, 0US90ZZ, 0US94ZZ, 0US9XZZ, 0W3Rx, 0W8NXZZ, 0WQNXZZ, 109x, 10A00ZZ, 10A03ZZ, 10A04ZZ, 10A07Z6, 10A07ZX, 10A07ZZ, 10A08ZZ, 10D0x, 10D1xZZ, 10Ex-10S0x, 10T20ZZ-10T24ZZ, 10Yx, 2Y44X5Z, 3027x, 3E030VJ, 3E033VJ, 3E040VJ, 3E043VJ, 3E050VJ, 3E053VJ, 3E060VJ, 3E063VJ, 3E0DXGC, 3E0E305-3E0E3TZ, 3E0E705, 3E0E729-3E0E7TZ, 3E0E805, 3E0E829-3E0E8TZ, 3E0P7GC, 4A0Hx, 4A0Jx, 4A1Hx, and 4A1Jx
- Received edoxaban during the index hospitalization or within 12 months prior to the index date
- Received multiple types of OACs during the index hospitalization

- Patients who died during the index hospitalizations

All the ICD-10 codes corresponding to the ICD-9 codes listed above will also be used to identify the conditions and procedures in the inclusion and exclusion criteria.

These inclusion and exclusion criteria are aligned with the Eliquis Harmonized Retrospective Study Protocol and are consistent with other previous apixaban retrospective database studies of patients with NVAf.

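### The pregnancy exclusion reads follow-up records and lists procedure codes not specific to pregnancy, and the recent joint-surgery exclusion accepts diagnosis codes that cannot date the surgery

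*Protocol*

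**What the plan says.** **Pregnancy.** Section 8.2.2 excludes patients who "Had medical claims indicating pregnancy at any time during the study period". Section 8.1 defines the period: "The overall study period will be from January 1, 2012 through September 30, 2017". Section 8.2 starts follow-up at discharge from the first qualifying stay, "with the corresponding hospital discharge date as the index date". The lead-in to section 8.2.2 reads: "Patients meeting any of the following criteria with the records in the index hospitalizations will not be included in the study". The ICD-9 procedure list for pregnancy is one block, 72 to 75.9. The ICD-10 procedure list includes the 10x codes but also 0DQPx to 0DQRx, 0TQBx, 0TQDx and a run containing "0US90ZZ, 0US94ZZ, 0US9XZZ, 0W3Rx, 0W8NXZZ, 0WQNXZZ". The criterion has no sex restriction and does not require a pregnancy diagnosis alongside a procedure code.

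**Joint replacement.** The same section excludes "hip or knee replacement surgery during the index hospitalizations or within a 6-week period prior to the index date". It identifies this from a list of procedure codes and also from ICD-9 diagnosis codes V43.64 and V43.65 and "ICD-10 diagnosis codes Z96.64x and Z96.65x".

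**Outcome.** Table 2 defines the primary outcome as a readmission in which bleeding is the first-listed discharge diagnosis.

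**The concern.** A cohort entry rule should use only what is known when follow-up starts. The pregnancy rule uses later records, and some of its procedure codes appear to cover treatment of bleeding. If so, the treatment given at a bleeding readmission can delete the patient and the event from the analysis. The lead-in points to a different window, so two programmers could build different cohorts from the same text.

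The joint rule has a different fault. It states a 6-week limit on surgery, but a diagnosis code on a hospital record carries the date of that stay, not of an operation. Patients whose joint was replaced years earlier could be dropped although the criterion does not mean them.

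**Working it through.** **1. Windows side by side (section 8.2.2)**

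| Exclusion | Window |
|---|---|
| Valve disease, valve replacement, dialysis or renal, VTE, reversible AF | Index stay or 12 months before the index date |
| Edoxaban | Index stay or 12 months before the index date |
| Hip or knee replacement | Index stay or 6 weeks before the index date |
| Several OACs; death | Index stay |
| Pregnancy | 1 January 2012 to 30 September 2017 |

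Only pregnancy runs past the index date. A patient indexed in 2013 can be removed by a record from 2017, and any patient by a record from the 1- or 3-month readmission window.

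**2. Code lists**

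The protocol defines none of these codes. Two things can be seen without a code book. The 0T prefix of 0TQBx and 0TQDx is the one the protocol itself uses under kidney procedures (0TS00ZZ, 0TYx). The joint rule lists its diagnosis codes separately from its procedure codes, and V43.64 and V43.65 share a family with V433, which the protocol uses as a diagnosis code for heart valve replacement. By the standard code set, 0W3R is control of bleeding in the genitourinary tract, and V43.64, V43.65, Z96.64x and Z96.65x are prosthesis-status codes. Both readings need confirmation in the code book.

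**3. The protocol's sample-size figure**

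With p1 = 0.014, p2 = 0.009, two-sided alpha 0.05 and power 80%:

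n per arm = (1.960·√(2 × 0.0115 × 0.9885) + 0.8416·√(0.014 × 0.986 + 0.009 × 0.991))² / 0.005² = 7,137

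Twice this is 14,274, the tabulated value at 80% power. The 95% row gives 11,815 per arm (2 × 11,815 = 23,630). At 30,000 per arm power exceeds 99%. Power is not the issue.

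**4. Effect of deleted events on the odds ratio**

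If a share f of the patients with an event is removed, the rate becomes p(1−f)/(1−pf) and the odds become p(1−f)/(1−p). The odds ratio is therefore multiplied by (1−f comparator)/(1−f apixaban). The intact value is (0.014/0.986)/(0.009/0.991) = 1.563. The shares below are assumed.

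| Loss, comparator vs apixaban | Odds ratio |
|---|---|
| Equal, any size | 1.563 |
| 2% vs 0% | 1.532 |
| 5% vs 2% | 1.516 |
| 5% vs 0% | 1.485 |

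**5. Illustrative size, pregnancy codes**

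The assumptions, none from the protocol, are:
- ICD-10 coding applies from October 2015, which is 21 of the 54 index months (0.39).
- 5–15% of major-bleeding readmissions are genitourinary or anorectal.
- 10–30% of those carry a listed code.

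Then f within the ICD-10 months is 0.05 × 0.10 = 0.5% to 0.15 × 0.30 = 4.5%. Expected events per 30,000 at 1.4% are 420. Events lost are 420 × 0.39 × 0.005 = 0.8 to 420 × 0.39 × 0.045 = 7.4, at most about 1.8%. If that maximum fell wholly on the comparator, the odds ratio would be 1.563 × 0.982 = 1.535.

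**6. Illustrative size, joint codes**

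If 5–10% of patients carry a prosthesis-status code (assumed), 1,500 to 3,000 per 30,000 are excluded. The remaining 27,000 or more per cohort, before matching attrition, still exceed 11,815 per arm.

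**The case against.** **Code meanings.** The protocol does not define the codes, so the bleeding and prosthesis readings come from outside it. That stands, which is why both are put as points to confirm. The window conflict, the missing sex restriction and the use of diagnosis codes for a dated operation do not depend on it.

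**The lead-in.** One can read it as confining every exclusion to index-stay records, in which case no readmission record counts. Read that literally, it would also cancel the 12-month and 6-week look-backs listed beneath it, so it cannot safely be taken to override the pregnancy window. The text needs reconciling under either reading.

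**Harmonized criteria.** Sections 8.2.1 and 8.2.2 say the codes and criteria follow a harmonized protocol used across apixaban database studies. This explains where the lists come from and gives consistency some value. It does not justify selecting on follow-up in a study whose endpoint is a bleeding readmission.

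**Size and type of effect.** The likely event loss is small, and equal loss leaves the odds ratio unchanged. The joint rule uses records up to the index date and applies the same way to all four cohorts, so it restricts the population rather than biasing the comparison. Both points stand.

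**Missed surgery.** Diagnosis codes may catch recent replacements done elsewhere, and section 8.9 says outpatient treatment and history are unavailable. That is a real cost of removing them.

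**Conclusion.** The point holds as a defect in two eligibility rules. The pregnancy rule makes inclusion depend on records after the start of follow-up, contradicts the section's lead-in and, if the code book confirms the meanings, can delete a primary event with its patient. The joint rule can exclude patients its own 6-week limit does not mean.

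Three stronger readings are not supported:
- A reader might infer that the primary comparison is materially biased. That needs unequal loss between drugs, and the protocol gives neither the share of events affected nor drug use by calendar period. Under the assumed rates, the extreme case moves the odds ratio from 1.563 to about 1.535.
- A reader might infer that every patient wrongly removed is an event. The window opens in January 2012, so a listed code at baseline, in the index stay or in a non-bleeding readmission also removes patients without an event.
- A reader might infer that the joint codes distort the drug comparison, or contradict the strength claimed in section 8.9. They mainly affect cohort size and who is represented, and that section only says that databases include patients, such as the elderly, who are often under-represented in trials.

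All affected shares are assumptions; the true numbers can only come from the database.

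**What to change.** - **Pregnancy window:** end the look-up at the index date (index stay or the 12 months before) and reword the lead-in to section 8.2.2 so that it agrees with the windows beneath it.
- **Pregnancy population and codes:** limit the rule to female patients. Check every listed ICD-10 procedure code against the code book, including the 2Y4, 3027, 3E0 and 4A groups, and remove those not specific to pregnancy. The 0W3R, 0TQ and 0DQ groups are the first to check.
- **Joint replacement:** drop V43.64, V43.65, Z96.64x and Z96.65x once confirmed as status codes, and identify recent surgery from the listed procedure codes with their dates.

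The work is one window edit and two code-list edits before the cohort is built. The costs are a small departure from the harmonized code set and some missed recent replacements done outside Premier hospitals; how many cannot be judged from the protocol. Counting by cohort the patients affected by each change would replace the assumed rates with actual ones.
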